# 14.2.3. Planned Subgroup Analyses

Appropriate interaction terms will be included in the primary regression analyses in order to conduct subgroup analyses according to DILI severity.

Between-group treatment effects will be provided for each subgroup, but interpretation of any subgroup effects will be based on the treatment-subgroup interaction and 95% confidence interval, estimated by fitting an appropriate interaction term in the regression models. Since the trial is powered to detect overall differences between the groups rather than interactions of this kind, these subgroup analyses will be regarded as exploratory.

# 15. Health Economics

Quality of Life will be measured using an online questionnaire to collect EQ-5D-5L data, with patients prompted by email / text message, and/or telephone. Patients who cannot use the online system will provide information by telephone

Quality of Life will be measured at 5 junctures for all participants: i) during initial DILI, ii) after DILI recovery prior to start of ATT, iii) 2 weeks after starting ATT, iv) one week after the end of ATT and v) at 12 months post-randomisation (the primary outcome). Participants with a DILI recurrence will have 2 additional measurements, vi) during DILI recurrence and vii) after recovery from DILI recurrence when on ATT. This is to enable assessment of the QoL impact of initial DILI (against a background of QoL detriment due to active TB and ATT, comparing i and ii), recurrent DILI (comparing vi and vii), TB disease under treatment (comparing ii and iii), and ATT (comparing iii and iv, and iii and v). The two arms of the trial will be compared using measurements i and v.

To enable healthcare resource costs to be calculated based on staff costs (determined by time and grade), drugs costs (from the British National Formulary), and costs of tests (NHS tariffs), we will record information on health services used by participants relevant to TB care during treatment and follow-up. This will include clinic visits, home visits, additional drugs used, and additional clinical resources required to manage recovery from DILI (e.g. ICU care). Relevance of services used to TB care will be determined by the attending TB team.

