#### 6.3. Blinding and concealment

Allocation will be concealed to trial staff prior to randomisation using REDCap, an automated web system operated by the NCTU.

Blinding of the participants and site research team following randomisation is not possible due to the nature of the interventions.

Table 3 provides an overview of the blinding status of all individuals involved in the management and delivery of the trial.

Trial role	Blinding status	Comments
Participant	Not blinded	Not possible due to the nature of the intervention.
		Participants will be informed
		which arm of the trial they
		have been randomised to
		immediately after
		randomisation.

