# 8. Trial procedures and assessments

#### 8.1. Summary of assessments

A summary of trial procedures is shown in figure 2. A detailed description of each procedure can be found in section 8.2.

Figure 2: Summary of trial procedures time point

Trial	TB-DILI Trial	Protocol	1.2	date:	02-Aug-2022	Page 30 of 58
name:		version:				

															TRIAI	L PERI	OD						
TIMEPOINTS	E	R	Pha	ise A						Pha	se B				Phase	e C		DIL	Recurrence		ЕоТ		Follow- up Post R
Timepoint [Weeks]	W-2	W-1				W0				W1	W2	W4	W6	W8	W16	W24	W32	Diagnosis	2-Weeks after	W25	W33	*	W52
Timepoint [Days]		-1	0	1	3	4	6	7	9									of DILI	treatment re-start				
Tolerance [Days]	а	±2	±1	±1	±1	±1	±1	±1	±1	±4	±4	±4	±4	±4	±14	±14	±14	-	-	-	-		-
ENROLMENT:																							
Eligibility screen	Х																						
Informed consent	Х																						
Baseline Assessments																							
Adjudication panel confirmation	Х																	Х					
EQ-5D-5L	Х																						
Randomisation		Х																					
CONTROL ARM																							
Drug Re-Introdcution																							
Reintroduce EH				Х																			
Reintroduce R						Х																	
Reintroduce Z								Х															
Drug Discontinuation																							
Discontinue Z+R														Х									
Assessments																							
LFT (suggested not mandated)			х		х		х		х	х	х	x	x	x	x	x	x	х	х				
EQ-5D-5L			Х								Х							Х	Х	Х			Х
Follow-Up post EoT																							
Follow-up telephone call																				Х		Х	
INTERVENTION ARM																							
Drug Re-Introdcution																							
Reintroduce EH				Х																			
Reintroduce R						Х																	
Drug Discontinuation																							
Discontinue R														Х									
Assessments																							
EQ.5D-5L			Х						_	Γ.	Х							Х	Х		Х		Х
Follow-Up post EoT						CI 31				_					 								
Follow-up telephone call					ľ	5.510	[														Х	Х	

E = Enrolment

R = Randomisation

EoT = End of Treatment

a. The enrolment period will occur at the onset of DILI, the period between E & R will be variable dependent upon patient recovery. Predicted average time is 2 weeks

\* Every 12 weeks after EoT until 12 months post R

Trial	TB-DILI Trial	Protocol	1.2	date:	02-Aug-2022	Page 32 of 58
name:		version:				

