## 9.1.2. Baseline Assessments

Prior to randomisation, all relevant clinical data will be submitted to the DILI-adjudication panel. The panel will review the clinical information to determine that the patient is experiencing/has experienced a DILI event related to treatment of TB with standard 4-drug ATT. The patient will also be asked to complete the EQ-5D-5L, a quality-of-life questionnaire.

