#### 9.1.3.Randomisation

Upon confirmation of DILI by the adjudication panel, randomisation will occur after the patient has recovered, and the attending clinician is prepared to re-commence treatment. The Principal Investigator or delegated site staff will randomise the patient using the online randomisation system via a secure website developed and maintained by NCTU.

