#### 9.1.4.Prescribe/ issue trial treatment

# Phase A

[Begins within 2 days of randomisation]

- Reintroduction of treatment regimen (anticipated duration):
  - o 9 days for control arm
  - 7 days for intervention arm

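### The only quality-of-life reading of the recovered, untreated state is nominally scheduled after open-label participants have been told their arm, and the protocol does not fix the order

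*Protocol*

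**What the plan says.** Section 15 sets five EQ-5D-5L readings for every participant. The first is during the initial DILI. The second is "ii) after DILI recovery prior to start of ATT". The others are two weeks into ATT (iii), one week after ATT ends (iv) and 12 months after randomisation (v). Reading ii is used in two contrasts: i with ii for the impact of the initial DILI, and ii with iii for TB disease under treatment. The arms are to be compared on readings i and v.

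Figure 2 in section 8.1 gives the timing. One EQ-5D-5L is at enrolment, where note a says "The enrolment period will occur at the onset of DILI". Section 9.1.2 agrees, placing it among the baseline assessments: "The patient will also be asked to complete the EQ-5D-5L, a quality-of-life questionnaire". The next EQ-5D-5L sits in the Day 0 column, entered separately in the control-arm and intervention-arm blocks. Randomisation is in the Day -1 column.

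Section 9.1.3 states that "randomisation will occur after the patient has recovered". Section 9.1.4 says of Phase A, which contains Day 0: "Begins within 2 days of randomisation". Section 6.3 states: "Blinding of the participants and site research team following randomisation is not possible due to the nature of the interventions". Its Table 3 adds that participants are told their arm straight after randomisation.

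**The concern.** A reading meant to describe the recovered patient before treatment is best taken when nothing about the allocated treatment can colour the answers. Here it is planned for a moment when the participant already knows whether they face the longer course without pyrazinamide or re-exposure to pyrazinamide.

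The protocol gives grounds to expect a reaction. Section 1.2.3 describes the choice as a possibly lower recurrence risk against 9 rather than 6 months of treatment, and section 1.2 says no quality-of-life data inform that balance. EQ-5D-5L is self-reported, so the news could shift answers or affect who completes the form.

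Two uses are exposed. The contrast of i with ii concerns an episode that is over before randomisation, yet its second value may include a response to allocation; the contrast of ii with iii inherits the same value. Cost-effectiveness is also a secondary objective, with follow-up counted from randomisation. Reading ii is the only recovered-state value near that origin, because reading i is taken during the acute episode, a variable time earlier (about two weeks on average, by note a).

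The exposure is avoidable. Randomisation waits for recovery, so every participant passes through a recovered, not yet allocated state. Later analysis cannot supply a pre-allocation value that was never collected.

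**Working it through.** The plan gives no figure for this point. The sample size (175 per arm, 157 analysed) rests on recurrence proportions and does not involve EQ-5D-5L. The check is therefore mainly one of order.

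**Step 1: match the entries in Figure 2 to its day header** ("Timepoint [Days] -1 0 1 3 4 6 7 9").

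| Event | Column | Tolerance | Resulting window |
|---|---|---|---|
| EQ-5D-5L at enrolment (i) | E, week -2 | variable, note a | before randomisation |
| Randomisation | Day -1 | ±2 | Day -3 to Day +1 |
| EQ-5D-5L, both arm blocks (ii) | Day 0 | ±1 | Day -1 to Day +1 |
| First reintroduction (EH) | Day 1 | ±1 | Day 0 to Day +2 |

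The nominal order is randomisation, disclosure, reading ii, treatment. Entry of reading ii within the arm-specific blocks supports this. The whole window for reading ii lies inside the randomisation window, so the tolerances permit either order.

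**Step 2: look for a rule elsewhere that settles the order.** Section 15 requires only recovery beforehand and ATT afterwards, which a reading on either side of randomisation satisfies. The Phase A text in section 9.1.4 mentions no questionnaire. Section 7.3 puts treatment start 1 to 3 days after randomisation, which leaves room for a post-allocation reading. No rule was found.

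**Step 3: confirm that a pre-allocation slot exists.** Section 9.1.3 puts recovery before randomisation. Section 15 collects the questionnaire online or by telephone, so moving it about one day earlier adds no reading and no visit.

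**Step 4: illustrate scale, on assumed inputs only.** The documents give no EQ-5D-5L mean, SD or expected shift. Assume that knowing the allocation moves reading ii by 0.01 to 0.03 in one arm.

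- Contrast pooled over a 1:1 trial: 0.01/2 = 0.005 to 0.03/2 = 0.015.
- Linear utility profile, Day 0 to week 2: shift × 0.5 × 14/365, which is 0.01 × 0.5 × 14/365 = 0.0002 to 0.03 × 0.5 × 14/365 = 0.0006 QALY.
- Adding a two-week segment from i to ii doubles this, to about 0.0004 to 0.0012 QALY.

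A shift in the same direction in both arms would not be halved in the pooled contrast, and would largely cancel between arms in a utility profile.

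**The case against.** The strongest reply is that section 15 compares the arms on i and v, and i precedes randomisation. No arm comparison on ii and no adjustment for ii is planned. This stands. A reader might infer that the trial's quality-of-life comparison has a contaminated baseline, or that adjusting for ii would remove part of the treatment effect. The documents do not support that; it would require an analysis they do not describe. The same applies to judging a shift against the standard error of an arm difference in ii: that comparison is not planned, and its SD would have to be assumed.

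Second, the sentence in section 15 is not itself wrong, and the overlapping tolerances make the Figure 2 order nominal. A reader might infer that every participant completes reading ii after learning the arm. That goes too far. But an order left to chance is also a defect, and the nominal plan is the unfavourable one.

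Third, reading ii feeds contrasts described without an arm split, so a one-arm shift is diluted, and its weight in a utility profile is small. This limits the size but does not remove the point.

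Fourth, the later readings are also self-reported with allocation known. That is unavoidable in an open-label trial. Reading ii differs because it can be taken before allocation.

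Fifth, making a self-completed form a condition of randomisation could delay restarting ATT, a delay that section 1.1 already treats as a harm of DILI. This stands and shapes the fix.

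**Conclusion.** The point holds in limited form. Figure 2 nominally schedules the only recovered, pre-treatment EQ-5D-5L reading after randomisation and disclosure. The tolerances allow the order to vary, and section 15 does not fix it. Reaction to allocation, or arm-related completion, could therefore enter the i-ii and ii-iii contrasts and any utility profile that uses ii.

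The between-arm comparison on i and v, the primary outcome and the sample size are unaffected. The size of any bias cannot be derived from the documents; under the assumed shift of 0.01 to 0.03 in one arm, the effects on the stated uses are small. The conclusion rests on the column alignment of Figure 2 and on Table 3's account of disclosure, not on the assumed shift. Priority is low to moderate: a modest weakness that is easily removed.

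**What to change.** In Figure 2 and section 15, move reading ii to the randomisation visit in both arms. Specify that it is completed after recovery is confirmed and before allocation is disclosed. Let this replace the Day 0 entry, so the number of readings is unchanged, and keep reading i as the acute-DILI value.

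State this as a required order of events, not as a condition for randomising: a missing questionnaire should not hold up randomisation. Record the completion time relative to randomisation so that late forms can be identified at analysis.

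The cost is a schedule edit, a time field and a small scheduling task for sites on the day of randomisation. The documents give no cost figure; that this is small is a judgement based on online or telephone collection.

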# (This table shows the summary for the main trial only. For details of the cohort study see Appendix A).

Title	Reintroduction of anti-tuberculosis therapy following drug-induced liver
	injury: a randomised controlled trial
Trial Design	Pragmatic, individually randomised, parallel group, open randomised controlled superiority trial with concealed allocation (1:1) and minimisation
Objectives	
 
Primary objective 
 
To determine if reintroduction of a non-pyrazinamide (Z)-containing anti-tuberculosis therapy (ATT) regimen results in a lower drug-induced liver injury (DILI) recurrence rate compared to a Z-containing ATT regimen in adults who have experienced an episode of DILI when being treated for active tuberculosis (TB)
 
 
 
Secondary objectives 
 
To determine the cost-effectiveness of reintroducing a non-Z containing, versus Z-containing regimen
 
 
 
Cohort study 
 
To determine i) the frequency and ii) quality of life impacts of DILI episodes in adults being treated for latent TB infection
 
 
 

Eligibility criteria	
 
Inclusion Criteria
 
Aged ≥18 years
 
Experienced DILI with standard 4-drug ATT for active pulmonary or extra-pulmonary TB
 
Medically suitable
 
for re-introduction of standard 4-drug ATT
 
Exclusion Criteria
 
Requirement for alternative ATT
 
Unable to provide written informed consent
 

Intervention and control	
 
Intervention         
 
Sequential full-dose reintroduction of a non-Z-containing 3-drug ATT regimen comprising ethambutol, isoniazid and rifampicin (EHR), as recommended by the American Thoracic Society (ATS) TB guideline
 
Control
 
Sequential full-dose reintroduction of a Z-containing 4-drug ATT regimen comprising ethambutol, isoniazid, rifampicin and pyrazinamide (EHRZ), as recommended by the National Institute for Health and Care Excellence (NICE) TB guideline
 
 
 

Trial	TB-DILI Trial	Protocol	1.2	date:	02-Aug-2022	Page 9 of 58
name:		version:				

Outcome	Primary

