Apart from any symptoms and sequelae related to DILI, a patient who experiences a DILI episode also suffers delay in the treatment of their primary illness. When a patient with active TB has a DILI episode, the overarching strategy is to i) stop the inciting drug(s), ii) allow the liver to recover and then iii) reintroduce as many first-line ATT drugs as possible to enable the highest chance of clinical cure of TB disease in the shortest length of time. The median duration of cessation of ATT is 18 days while reintroduction of ATT drugs takes a further 10 -14 days (median).2,12 Therefore, for each episode of DILI, a total of 28 days' delay can be expected before full ATT is re-started.12

Guiding the patient through recovery from DILI and re-establishment of ATT requires additional healthcare resources. In one study from Canada, 29 of 37 patients who developed serious ATT-related side effects made a total of 91 extra clinic visits, and the TB clinic nurses made an additional 30 home visits to 8 of these patients. If full standard first-line ATT is not reintroduced following DILI, modified regimens may require extension of the treatment duration beyond 6 months to achieve acceptable rates of clinical cure. This adds to patient and healthcare costs.

Trial	TB-DILI Trial	Protocol	1.2	date:	02-Aug-2022	Page 16 of 58
name:		version:				

Globally, rates of DILI following TB therapy of 2 - 25% are reported .14-18 In 2 UK studies, DILI was reported in about 7% of persons treated for TB; however, the definition of DILI differed between these studies.12,19

Roughly 53 - 57% of DILI episodes occur during the first 2 weeks of ATT, and 75 - 88% within the first 8 weeks, corresponding to the intensive phase of ATT.12,19-21

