# 3. Trial Design and Setting

#### 3.1. Trial Design

Phase III, multi-centre, randomised, open-label, parallel group, superiority trial with concealed allocation (1:1) and minimisation to receive either the intervention, sequential full-dose reintroduction of non-Z-containing 3-drug ATT (compromising EHR) or the control sequential full-dose reintroduction of a Z-containing 4-drug ATT (comprising EHRZ).

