#### EoT

• EQ5D questionnaire is completed one week after the end of treatment: This is expected to be W25 for control arm and W37 for intervention arm

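### Which borderline health services enter the cost comparison is left to the judgement of a treating team that knows the allocation

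*Protocol*

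**What the plan says.** Section 15 defines the data for costing: "we will record information on health services used by participants relevant to TB care during treatment and follow-up". It then lists categories: "This will include clinic visits, home visits, additional drugs used, and additional clinical resources required to manage recovery from DILI (e.g. ICU care". It closes with the rule at issue: "Relevance of services used to TB care will be determined by the attending TB team".

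Section 3.1 describes a "randomised, open-label, parallel group, superiority trial". Section 6.3 states: "Blinding of the participants and site research team following randomisation is not possible due to the nature of the interventions". Table 3 lists the principal investigator and site research staff as not blinded, and the health economist as blinded until after the final database lock.

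The data serve the one item listed under secondary objectives in the Trial Summary: "To determine the cost-effectiveness of reintroducing a non-Z containing, versus Z-containing regimen".

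On length of treatment, section 1.2.3 gives 9 months against 6. Section 9.1.4 times the end-of-treatment questionnaire as follows: "This is expected to be W25 for control arm and W37 for intervention arm". Figure 2 in section 8.1 places the same visit at W25 for control but W33 for intervention.

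**The concern.** The last sentence of section 15 is a rule about data capture, so it is not a detail left to an unseen analysis plan. On its plain wording, a service that the team considers unrelated to TB is not recorded. The rule has three weaknesses:

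- Relevance is a matter of opinion, and no criteria are given.
- The people giving the opinion know the regimen.
- They give it over a longer period of active treatment in one arm than in the other.

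The economic question is whether contacts saved through fewer recurrences offset the contacts and drugs added by longer treatment. If the threshold for calling a service TB-related differs between arms, the difference goes straight into the incremental cost. Whether liver injury is due to TB drugs is a similar attribution, and the protocol sends that one to a blinded Hepatic Adjudication Panel. The panel's remit is DILI episodes and their severity, not resource use.

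**Working it through.** **Does the deciding team know the arm?** Table 3 has no row for the attending TB team. That team prescribes a regimen with or without pyrazinamide, and sections 3.1 and 6.3 describe open treatment. The inference is secure.

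**Is there a blinded safeguard?** The health economist is blinded until lock, but can cost only what has already been recorded as relevant. The adjudication panel does not see resource use. None is stated.

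**How much longer is active care in the intervention arm?**

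- Section 9.1.4: W37 − W25 = 12 weeks.
- Figure 2: W33 − W25 = 8 weeks.
- Section 1.2.3: 9 − 6 = 3 months.

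The gap is 8 or 12 weeks depending on the place read. The two schedules must be reconciled.

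**Scale of the expected saving in contacts.** The protocol gives no figure for the cost comparison, so there is none to reproduce. The recurrence rates come from section 14.1.1 (10% and 1.5%). That calculation does reproduce: a two-sided pooled Z-test at 5% and 90% power needs 156 analysed per arm (157 stated), and 157 per arm gives 90.3% power.

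Section 1.1 cites a Canadian study in which "29 of 37 patients who developed serious ATT-related side effects made a total of 91 extra clinic visits", with a further 30 home visits by nurses.

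- Extra clinic visits per affected patient: 91/37 = 2.46.
- Adding home visits: (91 + 30)/37 = 121/37 = 3.27.
- Planned reduction in recurrence: 0.10 − 0.015 = 0.085.
- Contacts saved per randomised participant: 2.46 × 0.085 = 0.21, to 3.27 × 0.085 = 0.28.
- Equivalently, one contact per 1/0.278 = 3.6 to 1/0.209 = 4.8 participants.

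**What differential would match it?** The shift in mean contacts equals the number of borderline services per participant times the between-arm difference in the share judged relevant. The documents give neither. Assume, for range only, a difference of 5 to 20 percentage points. The number of borderline services per participant needed to equal the saving is then:

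- at 20 points: 0.209/0.20 = 1.0 to 0.278/0.20 = 1.4
- at 5 points: 0.209/0.05 = 4.2 to 0.278/0.05 = 5.6

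**Limits of the illustration.** The cited study covers all serious side effects of TB drugs, and its use for DILI recurrence is an assumption. It counts clinic and home visits, which section 15 already names for inclusion. It therefore shows how small the saving is, not how much could be misclassified. It leaves out the contacts added by longer treatment, and all drugs, tests and intensive care, so it is not an estimate of incremental cost.

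**The case against.** The strongest reply is that the main cost drivers are protected. Section 15 names them, section 4.2 asks sites to upload every liver test performed, and section 7.3 puts medication start and stop dates in the eCRF. Counting only disease-related costs is also a legitimate choice. This stands, and it confines the concern to borderline items. A reader might infer that the team decides which costs enter each arm as a whole; the text does not support that.

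A reader might also infer that costs will be over-attributed in the intervention arm, because the team is still treating those patients. No passage shows this. Contacts during the extra months on treatment are a real cost of the longer regimen. Recording also runs through follow-up in both arms, with calls at end of treatment and every 12 weeks until 12 months. The possibility of bias stands; its direction does not.

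Dividing all 121 contacts by the 29 patients who made extra clinic visits would give 4.2 per event and a saving of 0.35. That is the wrong denominator, since 37 patients had the event.

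Nor is the loss of data wholly irreversible. Sections 9.3.2 and 9.4 foresee data from medical records and NHS Digital, which leaves a partial route to recovery.

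**Conclusion.** The point holds in limited form. Section 15 puts an unblinded judgement without criteria between what participants use and what is costed, and treatment length differs by arm while that judgement is made. It can bias the incremental cost in a named secondary objective. The documents do not allow the direction or size of the bias to be stated.

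The only scale available is illustrative: 0.21 to 0.28 contacts saved per randomised participant, if the cited side-effect contacts carry over to recurrences and the planned 8.5-point reduction occurs. A quantity that small is sensitive to differential classification, but the differential needed to cancel it is not trivial. The primary outcome and the sample size are not touched. This is a cheap improvement and best made prospectively, because services that were never recorded may be only partly recoverable.

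**What to change.** Replace the last sentence of section 15 with three elements:

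- **A prespecified list of service types**, recorded for every participant in both arms from randomisation to 12 months. For example: TB and hepatology clinic visits, home visits, hospital admissions and ICU days, liver tests, and anti-TB and DILI-related drugs.
- **A written, arm-independent rule** for what counts as TB-related in the base-case costing, based on service type and recorded reason. It should not depend on whether the participant is still on treatment, since that would bring the arm back in. Contacts due to longer treatment must still be counted.
- **The team's opinion as a recorded flag**, not a filter, with all listed services costed as a sensitivity analysis.

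Blinded classification by the health economist is not a workable substitute. Item-level drugs and dates would reveal the arm, and Table 3 bars that role from potentially unblinding data until after lock.

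Separately, reconcile the intervention-arm end-of-treatment week between section 9.1.4 and Figure 2.

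The cost is a change to protocol and eCRF wording, some extra data entry (more where admissions fall outside the TB service), and somewhat more variable totals in the sensitivity analysis. No extra participant visits are needed.
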